11.4 Risks

Risks to the subjects are associated with venipuncture, topical anesthetic cream, and study agent(s). These risks are outlined below. In addition, questions asked regarding a subject's use of contraception may make the subject uncomfortable. These questions will be asked in a private area and the subject will be made aware that he or she does not have to answer any question that they do not feel comfortable answering. Because this is a live vaccine, there is an assumed risk to the fetus should the mother receive the vaccine when pregnant. The vaccine virus is highly attenuated and is expected to have only minimal replication in the host. Nevertheless, female subjects will be cautioned of the unknown risk of study agents to the fetus and will be advised to use effective birth control methods for the duration of the study. Current evidence does not suggest any risk to the fetus should a woman become pregnant after clearing infectious ZIKV

from the blood. For this reason, the vaccine should not pose any risk to the fetus should a subject become pregnant after clearing infectious vaccine virus from the blood (presumed to be approximately day 16 and after post-vaccination).

11.4.1 Venipuncture

The total amount of blood to be drawn throughout the 6-month duration of the primary study is approximately 500 mL. Risks occasionally associated with venipuncture include excessive bleeding, pain, bruising, or hematoma at the site of venipuncture, lightheadedness, and syncope (rarely). Infection may occur rarely.

11.4.2 Risk of Use of Vaginal Cup

The vaginal cup is a commercially-available product used during menstruation. It is contraindicated in women with an intrauterine device (IUD) in place. For women who have an IUD in place, vaginal secretion specimens will be collected by use of vaginal swab.

11.4.3 Topical Anesthetic Cream

Risks occasionally associated with the use of topical anesthetic cream include temporary skin discoloration, skin irritation, rash, hives, and rarely, dizziness or drowsiness.

11.4.4 Inoculation

Possible local vaccine reactions include pain, swelling, or erythema for 2 to 3 days, lymphadenopathy, or pruritus at the injection site. Potential systemic reactions that may occur include symptoms of ZIKV such as rash, fever, headache, non-purulent conjunctivitis, generalized myalgias, and arthralgias. Immediate hypersensitivity reactions including urticaria, anaphylaxis, or other IgE-mediated responses are possible, as with any vaccine. Guillain-Barre syndrome has been reported in persons infected with wt ZIKV.

11.4.5 Other Risks

Subjects may be asked to defer routine immunization (such as influenza) with live vaccines 28 days prior or killed vaccines 14 days prior to inoculation or until after 28 days following inoculation, with the exception of COVID-19 vaccines. This may increase the risk that the subject will be infected with an influenza virus during this period. As with any investigational vaccine, there is a theoretical possibility of risks about which we have no present knowledge. Subjects will be informed of any such risks should further information become available.

11.5 Benefits

Subjects will not receive any direct benefit from participation in this study. They will receive a physical examination and laboratory screening for HIV infection, hepatitis B infection, and hepatitis C infection. They may potentially develop antibodies against ZIKV virus. It is hoped that information gained in this study will contribute to the development of a safe and effective vaccine for the prevention of ZIKV infection and to a better understanding of the protective immune response to ZIKV infection.

11.6 Compensation

Subjects will be compensated up to \$80 for screening, up to \$150 for inoculation day, and up to \$80 for each completed scheduled follow-up visit. They will also receive up to a \$250 bonus if all study visits are completed on time. Subjects will be compensated for the screening only if

they are enrolled in the study. Subjects will only be compensated for the visits that they complete. In addition, should subjects be asked to return to the clinic after Study Day 180 for collection of vaginal secretions (women) or semen (men), they will be compensated up to \$80.00 for each additional visit. Alternates who come to the clinic on vaccination day but who are not vaccinated due to fulfillment of enrollment for that day will be compensated up to \$150. Subjects enrolled in the study will receive a maximum total compensation of up to \$1,520 if they complete all scheduled visits. Subjects will receive additional compensation, described above, if they complete additional visits as required by the protocol.

11.6.1 Compensation for Injury

The services at the Johns Hopkins Hospital, the Johns Hopkins Bayview Medical Center, or the University of Vermont Medical Center will be available to subjects who require inpatient care for any injury resulting from participation in the trial. This short-term medical care will be paid for through our contract with NIH. Short-term medical care will be given at a facility determined by JHU/UVM and NIH. No long-term medical care or financial compensation for research-related injuries will be offered by the Johns Hopkins University, Johns Hopkins Hospital, the NIH, or the federal government.

11.7 Confidentiality

All study-related information will be stored securely at the study site. All subject information will be stored in locked file cabinets in areas with access limited to study staff. All laboratory specimens, reports, study data collection, and process and administrative forms will be identified by coded number only to maintain subject confidentiality. Computer entry will be done using a study ID number for each subject and all local databases will be secured with password-protected access systems. Forms, lists, logbooks, appointments books, and any other listings that link subject study ID numbers to other identifying information will be stored in a separate, locked file in an area with limited access. A subject's study information will not be released without the written permission of the subject, except as necessary for monitoring by the Sponsor and/or its contractors and the FDA.

11.8 Biohazard Containment

As the transmission of HIV and other blood-borne pathogens can occur through contact with contaminated needles, blood, and blood products, appropriate blood and secretion precautions will be employed by all personnel during the drawing of blood and shipping and handling of all specimens for this study, as currently recommended by the Centers for Disease Control and Prevention and the NIH.

All infectious specimens will be transported using packaging mandated in the Code of Federal Regulations, 42 CFR Part 72. Please also refer to individual carrier guidelines (e.g., Federal Express, Airborne Express) for specific instructions.

12 PUBLICATION POLICY

The International Committee of Medical Journal Editors (ICMJE) member journals have adopted a trials' registration policy as a condition for publication. This policy requires that all clinical trials be registered prior to enrollment of any subject in a public trials registry, such as ClinicalTrials.gov, which is sponsored by the National Library of Medicine. The ICMJE defines a clinical trial as any research project that prospectively assigns human subjects to intervention

or comparison groups to study the cause-and-effect relationship between a medical intervention and a health outcome. Studies designed for other purposes, such as to study pharmacokinetics or major toxicity, would be exempt from this policy.

14 APPENDICES

14.1 Appendix 1: Adverse Event Grading Table¹

Event	Grade I – Mild	Grade II – Moderate	Grade III - Severe	Grade IV – Life Threatening
General Severity Grading	Event that is easily tolerated, may require 1 dose of medication/treatment	Event that interferes with daily activity or requires more than 1 dose of medication/treatment	Event that prevents daily activity and requires medical intervention	Event that has life threatening consequences and/or urgent intervention is indicated
Local Reactogenicity	Grade I – Mild	Grade II – Moderate	Grade III - Severe	Grade IV – Life Threatening
Injection Site Tenderness	Tenderness that is easily tolerated	Tenderness that interferes with daily activity	Tenderness that prevents daily activity	Life-threatening consequences; urgent intervention indicated
Injection Site Pain	Pain that is easily tolerated	Pain that interferes with daily activity	Pain that prevents daily activity	Life-threatening consequences; urgent intervention indicated
Injection Site Pruritus	Pruritus that is easily tolerated	Pruritus that interferes with daily activity	Pruritus that prevents daily activity	Life-threatening consequences; urgent intervention indicated
Injection Site Induration	> 0 - 20 mm	> 20 - 50 mm	> 50 mm	Life-threatening consequences; urgent intervention indicated
Injection Site Erythema	> 0 - 20 mm	> 20 - 50 mm	> 50 mm	Life-threatening consequences; urgent intervention indicated
Systemic Reactogenicity	Grade I – Mild	Grade II – Moderate	Grade III - Severe	Grade IV – Life Threatening
Fever (Oral)	100.4° F – 101.4°F	101.5°F – 102.4°F	≥ 102.5°F	-

Event	Grade I – Mild	Grade II – Moderate	Grade III - Severe	Grade IV – Life Threatening
Headache	Headache that is easily tolerated, may require 1 dose of medication/treatment	Headache that interferes with daily activity or requires > 1 dose of medication	Headache that prevents daily activity	Life-threatening consequences; urgent intervention indicated
Retro-orbital Pain (ROP)	ROP that is easily tolerated, may require 1 dose of medication/treatment	ROP that interferes with daily activity or requires > 1 dose of medication	ROP that prevents daily activity	Life-threatening consequences; urgent intervention indicated
Non-purulent Conjunctivitis	Easily tolerated, may require 1 dose of medication/treatment	Interferes with daily activity or requires > 1 dose of medication/treatment	Prevents daily activity	Life-threatening consequences; urgent intervention indicated
Photophobia	Photophobia that is easily tolerated, may require 1 dose of medication/treatment	Photophobia that interferes with daily activity or requires > 1 dose of medication	Photophobia that prevents daily activity	Life-threatening consequences; urgent intervention indicated
Nausea	Nausea that is easily tolerated	Nausea that interferes with daily activity or requires > 1 dose of medication	Nausea that prevents daily activity	Life-threatening consequences; urgent intervention indicated
Fatigue	Fatigue that is easily tolerated, may require 1 dose of medication/treatment	Fatigue that interferes with daily activity or requires > 1 dose of medication	Fatigue that prevents daily activity	Life-threatening consequences; urgent intervention indicated
Myalgia	Myalgia that is easily tolerated, may require 1 dose of medication/treatment	Myalgia that interferes with daily activity or requires > 1 dose of medication	Myalgia that prevents daily activity	Life-threatening consequences; urgent intervention indicated

Event	Grade I – Mild	Grade II – Moderate	Grade III - Severe	Grade IV – Life Threatening
Arthralgia	Arthralgia that is easily tolerated, may require 1 dose of medication/treatment	Arthralgia that interferes with daily activity or requires > 1 dose of medication	Arthralgia that prevents daily activity	Life-threatening consequences; urgent intervention indicated
ZIKV-like Rash	Rash is present but asymptomatic	Rash is symptomatic (pruritus/pain) but does not interfere with function	Rash is symptomatic and interferes with function	Life-threatening consequences; urgent intervention indicated
Solicited Lab AEs	Grade I – Mild	Grade II – Moderate	Grade III - Severe	Grade IV – Life Threatening
Leukopenia	2,500 - 3,500/mm ³	1,500 - 2,499/mm ³	1,000 - 1,400/mm ³	Life-threatening consequences; urgent intervention indicated
Neutropenia (Reduced ANC) ²	≥ 750 - 999/mm3	≥ 500 - 749/mm3	≤ 500/mm3	Life-threatening consequences; urgent intervention indicated
Thrombocytopenia (Reduced Platelets)	100,000 – 120,000/mm3	75,000 - 99,999/ mm3	≤ 74,999/mm3	Life-threatening consequences; urgent intervention indicated
Other Laboratory Values	Grade I – Mild	Grade II – Moderate	Grade III - Severe	Grade IV – Life Threatening
Leukocytosis (Increased WBCs)	11,500 - 13,000/mm3	13,001 - 15,000/mm3	≥ 15,000 or < 1,000/mm3	Life-threatening consequences; urgent intervention indicated
Hemoglobin (female)	9.5 - 10.7 gm/dL	8.0 - 9.4 gm/dL	≤ 7.9 gm/dL	Life-threatening consequences; urgent intervention indicated
Hemoglobin (male)	11.0 - 12.5 gm/dL	9.0 – 10.9 gm/dL	≤ 8.9 gm/dL	Life-threatening consequences; urgent intervention indicated -

Event	Grade I – Mild	Grade II – Moderate	Grade III - Severe	Grade IV – Life Threatening
PT	> 1.0 - 1.25 x ULN	> 1.25 - 1.5 x ULN	> 1.5 x ULN	Life-threatening consequences; urgent intervention indicated
PTT	> 1.0 - 1.66 x ULN	> 1.66 - 2.33 x ULN	> 2.33 x ULN	Life-threatening consequences; urgent intervention indicated -
ALT	> 1.25 - 2.5 x ULN	> 2.5 - 5.0 x ULN	> 5.0 x ULN	Life-threatening consequences; urgent intervention indicated -
Creatinine	1.5 - 1.7 mg/dL	> 1.7 – 2.0 mg/dL	> 2.0 mg/dL	Life-threatening consequences; urgent intervention indicated -
Fibrinogen, Decreased	100 mg/dL to < lower limit of normal (LLN)	50 - 99 mg/dL	<50 mg/dL, or associated with gross bleeding, or associated with disseminated coagulation	Life-threatening consequences; urgent intervention indicated -
Fibrinogen, Increased	> ULN to 600 mg/dL	> 600 mg/dL	N/A	Life-threatening consequences; urgent intervention indicated
Creatine phosphokinase (CPK)	≥ 4 x ULN- 6 x ULN	> 6 x ULN- 10 x ULN	> 10 x ULN	Life-threatening consequences; urgent intervention indicated
Sodium: Hyponatremia	130 – 134 mEq/L	123 – 129 mEq/L	< 122 mEq/L	Life-threatening consequences; urgent intervention indicated -
Sodium: Hypernatremia	145 – 150 mEq/L	151 – 157 mEq/L	> 158 mEq/L	Life-threatening consequences; urgent intervention indicated -

Event	Grade I – Mild	Grade II – Moderate	Grade III - Severe	Grade IV – Life Threatening
Potassium: Hypokalemia	3.1 – 3.2 mEq/L	2.9 – 3.0 mEq/L	< 2.8 mEq/L	Life-threatening consequences; urgent intervention indicated -
Potassium: Hyperkalemia	5.2 – 5.5 mEq/L	5.6 – 6.0 mEq/L	> 6.1 mEq/L	Life-threatening consequences; urgent intervention indicated
Phosphate: Hypophosphatemia	2.0 – 2.2 mg/dL	1.5 – 1.9 mg/dL	< 1.4 mg/dL	Life-threatening consequences; urgent intervention indicated -
Calcium (Corrected for Albumin): Hypocalcemia	1.95 – 2.04 mmol/L	1.75 – 1.94 mmol/L	< 1.74 mmol/L	Life-threatening consequences; urgent intervention indicated
Calcium (Corrected for Albumin): Hypercalcemia	2.51 – 2.88 mmol/L	2.89 – 3.13 mmol/L	> 3.14 mmol/L	Life-threatening consequences; urgent intervention indicated
Magnesium: Hypomagnesemia	0.60 – 0.74 mmol/L	0.45 – 0.59 mmol/L	< 0.44 mmol/L	Life-threatening consequences; urgent intervention indicated
Bilirubin (hyperbilirubinemia)	> 1.0 – 1.5 x ULN	> 1.5 – 2.5 x ULN	> 2.5 ULN	Life-threatening consequences; urgent intervention indicated -
Glucose: Hypoglycemia (Nonfasting, No Prior Diabetes)	55 – 69 mg/dL	40 – 54 mg/dL	<39 mg/dL	Life-threatening consequences; urgent intervention indicated
Glucose: Hyperglycemia (Nonfasting, No Prior Diabetes)	116 – 160 mg/dL	161 – 250 mg/dL	> 251mg/dL	Life-threatening consequences; urgent intervention indicated

Event	Grade I – Mild	Grade II – Moderate	Grade III - Severe	Grade IV – Life Threatening
Triglycerides	—	400 – 750 mg/dL	> 751 mg/dL	Life-threatening consequences; urgent intervention indicated -
Liver Transaminase (LFTs) GGT AST Alk Phos	> 1.25 – 2.5 x ULN > 1.25 – 2.5 x ULN > 1.25 – 2.5 x ULN	> 2.5 – 5.0 x ULN > 2.5 – 5.0 x ULN > 2.5 – 5.0 x ULN	> 5.0 x ULN > 5.0 x ULN > 5.0 x ULN	Life-threatening consequences; urgent intervention indicated
Pancreatic Amylase Lipase	> 1.0 – 1.5 x ULN > 1.0 – 1.5 x ULN	> 1.5 – 2.0 x ULN > 1.5 – 2.0 x ULN	> 2.0 x ULN > 2.0 x ULN	Life-threatening consequences; urgent intervention indicated -
Other Cardiovascular	Grade I – Mild	Grade II – Moderate	Grade III - Severe	Grade IV – Life Threatening
Cardiac Arrhythmia	Asymptomatic; transient dysrhythmia, no therapy required	Recurrent/persistent dysrhythmia; symptomatic therapy required	unstable dysrhythmia, hospitalization and therapy required	Life-threatening consequences; urgent intervention indicated
Hypertension	Transient, increase > 20 mm Hg diastolic BP; no therapy required	Recurrent; chronic increase > 20 mm Hg diastolic BP; therapy req.	acute therapy required outpatient or hospitalization possible	Life-threatening consequences; urgent intervention indicated
Hypotension	Transient orthostatic hypotension with heart rate increased by 20 beats/min or decreased by < 10 mm Hg systolic BP, no therapy required	Symptoms or BP decreased by < 20 mm Hg systolic, correctable with oral fluid therapy	Mean arterial pressure < 60 mm Hg, IV fluids required, or hospitalization	Life-threatening consequences; urgent intervention indicated
Pericarditis	Mild/moderate asymptomatic effusion, no therapy	Symptomatic effusion, pain, EKG changes	Tamponade or pericardiocentesis or surgery required	Life-threatening consequences; urgent intervention indicated

Event	Grade I – Mild	Grade II – Moderate	Grade III - Severe	Grade IV – Life Threatening
Hemorrhage, Blood Loss	Minimal blood loss, asymptomatic, no therapy required	Symptomatic blood loss and no transfusion required	Massive blood loss or > 2 units transfused Symptomatic AND transfusion of 1-2 units of blood or packed red cells	Life-threatening consequences; urgent intervention indicated
Other Gastrointestinal	Grade I – Mild	Grade II – Moderate	Grade III - Severe	
Vomiting	Mild or transient; 2 – 3 episodes per day or mild vomiting lasting < 1 week	Moderate or persistent; 4 – 5 episodes per day; or vomiting lasting ≥ 1 week, therapy required	Severe vomiting of all food/fluids in 24 hours or orthostatic hypotension or IV therapy required	Life-threatening consequences; urgent intervention indicated
Diarrhea	Mild or transient; 3 - 4 loose stools per day or mild diarrhea lasting less than 1 week	Moderate or persistent; 5 - 10 loose stools per day or diarrhea lasting ≥ 1 week, therapy required	> 10 loose stools/day bloody diarrhea; or orthostatic hypotension or electrolyte imbalance, > 2 L IV fluid required	Life-threatening consequences; urgent intervention indicated
Oral Discomfort/Dysphagia	Difficulty swallowing but able to eat and drink	Unable to swallow solids	Unable to drink fluids; IV fluids required	Life-threatening consequences; urgent intervention indicated
Constipation	Constipation less than 78 hours and requires medication for relief	Moderate abdominal pain 78 hours with impaction, requiring therapy	Requiring disimpaction or hospital treatment	Life-threatening consequences; urgent intervention indicated
Other Respiratory	Grade I – Mild	Grade II – Moderate	Grade III - Severe	Grade IV – Life Threatening
Bronchospasm Acute	Transient; no therapy; FEV1 or peak flow reduced to 70- < 80%	Therapy required; normalizes with bronchodilator; FEV1 or peak flow 50 - 69%	No normalization with bronchodilator; FEV1 or peak flow 25 – 49%, retractions	Life-threatening consequences; urgent intervention indicated

Event	Grade I – Mild	Grade II – Moderate	Grade III - Severe	Grade IV – Life Threatening
Dyspnea	Dyspnea on exertion	Dyspnea with normal activity	Dyspnea at rest	Life-threatening consequences; urgent intervention indicated
Other Neurologic	Grade I – Mild	Grade II – Moderate	Grade III - Severe	Grade IV – Life Threatening
Nuchal Rigidity	--	--	Presence of Nuchal rigidity	Life-threatening consequences; urgent intervention indicated
Neuropsychological	Mild confusion or cognitive impairment	Moderate confusion or cognitive impairment	Severe confusion or cognitive impairment	Life-threatening consequences; urgent intervention indicated
Neurocerebellar	Slight incoordination or dysdiadochokinesia	Intention tremor, dysmetria, slurred speech, or nystagmus	Ataxia requiring assistance to walk or arm incoordination interfering with ADLs	Life-threatening consequences; urgent intervention indicated
Neuromotor	Mild weakness in muscle of feet, but able to walk; and/or mild increase in reflexes	Moderate weakness in feet or legs, e.g. unable to perform deep knee bend, mild weakness in hands, loss of previously present reflex or development of hyperreflexia.	Marked distal weakness	Life-threatening consequences; urgent intervention indicated
Neurosensory	Mild impairment (decreased sensation in focal area or symmetrical distribution)	Moderate symmetrical impairment, mild impairment that is not symmetrical	Severe impairment (decreased or loss of sensation to knees or wrists) or loss of sensation of at least moderate degree in multiple areas or functions	Life-threatening consequences; urgent intervention indicated

Event	Grade I – Mild	Grade II – Moderate	Grade III - Severe	Grade IV – Life Threatening
Paresthesia (Burning, Tingling, etc.)	Mild discomfort; no therapy required	Moderate discomfort; non-narcotic analgesia required	Severe discomfort; or narcotic analgesia required with symptomatic improvement	Life-threatening consequences; urgent intervention indicated
Other Dermatologic	Grade I – Mild	Grade II – Moderate	Grade III - Severe	Grade IV – Life Threatening
Dermatitis	Rash is present but asymptomatic	Rash is symptomatic (pruritus/pain) but does not interfere with function	Rash is symptomatic and interferes with function	Life-threatening consequences; urgent intervention indicated
Other Urinalysis	Grade I – Mild	Grade II – Moderate	Grade III – Severe	Grade IV – Life Threatening
Proteinuria: Random Urine	1+	2+ - 3+	4+	-
Proteinuria: 24 Hour Urine	200 mg – 1 g loss/day or < 0.3% or < 3 g/L	> 1 – 2 g loss/day or 0.3% - 1.0% or 3 – 10 g/L	> 2 g loss/day or > 1.0% or > 10 g/L	-
Hematuria (In the Absence of Vaginal Bleeding)	Microscopic only, 6-10 rbc/hpf	> 10 rbc/hpf	Gross, with or without clots; or RBC casts	Life-threatening consequences; urgent intervention indicated
Other Miscellaneous	Grade I – Mild	Grade II – Moderate	Grade III - Severe	Grade IV – Life Threatening
Malaise	Malaise that is easily tolerated	Malaise that interferes with daily activity	Malaise that prevents daily activity	Life-threatening consequences; urgent intervention indicated

¹Grade 4 will be assigned to any AE that is determined to be potentially life-threatening. Grade 5 will be assigned to any AE that results in death

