8.5.1.1 Halting for Unacceptable Reactogenicity

Following administration of rZIKV/D4Δ30-713, the following criteria will be used to define unacceptable reactogenicity of the rZIKV/D4Δ30-713 vaccine:

1. One or more subjects experience an SAE (as defined in Section 8.1.6 of this protocol) that is determined to be possibly, probably, or definitely related to the administered vaccine (as defined in Section 8.2.4. of this protocol);
2. One or more subjects experience anaphylaxis that is possibly, probably or definitely related to the administered vaccine;
3. One or more subjects experience a Grade 4 adverse event that is definitely, probably, or possibly related to the administered vaccine;
4. Two or more subjects experience the same objective physical finding of severity Grade 3 that is definitely, probably, or possibly related to the administered vaccine, with the exception of Grade 3 erythema at the injection site, as defined in Section 8.2.3. of this protocol;
5. Two or more subjects experience the same Grade 3 laboratory abnormality that is possibly, probably, or definitely related to the administered vaccine;
6. Two or more subjects experience an ANC $\geq 500/\text{mm}^3$ but $< 750/\text{mm}^3$ for > 5 days duration¹;
7. Two or more subjects experience an ANC $< 500/\text{mm}^3$ for any duration¹; or
8. Two or more subjects experience a vaccine-associated Zika-like syndrome, defined as an infection² associated with fever and 2 or more of the following symptoms:
 - a. Grade 2 or greater headache lasting ≥ 12 hours
 - b. Grade 2 or greater photophobia lasting ≥ 12 hours
 - c. Grade 2 or greater generalized myalgia lasting ≥ 12 hours

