14.2 Appendix 2: Brighton Criteria for Guillain-Barré Syndrome

Level 1 of diagnostic certainty	Level 2 of diagnostic certainty	Level 3 of diagnostic certainty
 Bilateral and flaccid weakness of the limbs	 Bilateral and flaccid weakness of the limbs	 Bilateral and flaccid weakness of the limbs
 Decreased or absent deep tendon reflexes in weak limbs	 Decreased or absent deep tendon reflexes in weak limbs	 Decreased or absent deep tendon reflexes in weak limbs
 Monophasic illness pattern; and interval between onset and nadir of weakness between 12 hours and 28 days; and subsequent clinical plateau	 Monophasic illness pattern; and interval between onset and nadir of weakness between 12 hours and 28 days; and subsequent clinical plateau	 Monophasic illness pattern; and interval between onset and nadir of weakness between 12 hours and 28 days; and subsequent clinical plateau
 Cytoalbuminologic dissociation (i.e. laboratory normal value and CSF total laboratory normal value and CSF total white cell count < 50 cells/ μ L	 Absence of identified alternative diagnosis for weakness	 Absence of identified alternative diagnosis for weakness
 Electrophysiological findings consistent with GBS	 CSF total white cell count < 50 cells/ μ L (with or without CSF protein elevation above laboratory normal value); OR electrophysiological studies consistent with GBS if CSF not collected or results not available	

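### Two Appendix 1 grading rows are mis-bounded: leukopenia skips a WBC of 1,401 to 1,499/mm³, and hypotension sets only upper limits on the systolic fall, so a worse value can take no row grade or a lower one

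*Combined protocol and SAP*

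**What the plan says.** Appendix 1 (Section 14.1) numbers its grades in Roman numerals; Arabic numerals are used here.

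**Leukopenia row.** Grade 1 is 2,500 to 3,500/mm³, Grade 2 is 1,500 to 2,499 and Grade 3 is 1,000 to 1,400. Counts under 1,000 appear only in the Grade 3 cell of the Leukocytosis row, "≥ 15,000 or < 1,000/mm3". Neither Table 9 nor Table 11 lists leukopenia, so Section 8.2.3 sends it to Appendix 1.

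**Hypotension row.**
- Grade 1: "Transient orthostatic hypotension with heart rate increased by 20 beats/min or decreased by < 10 mm Hg systolic BP, no therapy required"
- Grade 2: "Symptoms or BP decreased by < 20 mm Hg systolic, correctable with oral fluid therapy"
- Grade 3: "Mean arterial pressure < 60 mm Hg, IV fluids required, or hospitalization"

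**Generic scales.** Table 10 (Section 8.2.3) and the General Severity Grading row that opens Appendix 1 both give Grade 1 to an easily tolerated event needing at most one dose of treatment.

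**Where the grades are used.** Intensity is part of the primary safety endpoint (Precis, Primary Endpoints), and Section 10.3 classifies related events by severity. Halting item 5 in Section 8.5.1.1 reads: "Two or more subjects experience the same Grade 3 laboratory abnormality that is possibly, probably, or definitely related to the administered vaccine".

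**The concern.** A grading row should give each value exactly one grade, and a worse value should never take a lower grade than a milder one. These two rows do neither as printed.

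Leukopenia matters more, because a laboratory grade feeds a halting rule: a count in the gap lies closer to the Grade 3 band than most Grade 2 counts do, yet is not Grade 3. It can also affect follow-up. The Day 21 blood count in Section 7.4.1 is repeated only if an earlier result, WBC included, is Grade 1 or above and unresolved. For hypotension, the severity tables could show a larger fall as ungraded, or graded below a smaller one.

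**Working it through.** The plan states no figure to reproduce. The check applies the printed bounds to values and reads off the grades.

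**Leukopenia** (inputs: Appendix 1, Leukopenia row)

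- Gap between Grade 2 (1,500 and above) and Grade 3 (1,400 and below): 1,401 to 1,499, which is 1,499 − 1,401 + 1 = 99 whole-number counts.
- Reported to the nearest 100/mm³, the neighbouring values are 1,400 (Grade 3) and 1,500 (Grade 2), so no value falls in the gap.
- Reported to the nearest 10/mm³, nine values do: 1,410, 1,420, and so on to 1,490.
- Order as the count falls, with the generic scale filling the gap: 2,000 is Grade 2, a well-tolerated 1,450 is Grade 1, and 1,300 is Grade 3.
- Halting item 5: two subjects with related counts of 1,400 meet it; two with related counts of 1,450 contribute nothing to it.
- Day 21 repeat: by the row alone, an unresolved 1,450 triggers no repeat while an unresolved 3,400 does. With the generic scale, 1,450 also triggers one. The text does not say which reading applies.
- Exposure: Appendix 4 schedules a CBC at Days 4, 6, 8, 10, 12, 14 and 16, seven post-dose visits.

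**Hypotension** (inputs: Appendix 1, Hypotension row)

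Assume no symptoms, mean arterial pressure of at least 60, no IV fluids and no hospitalization, and set the therapy wording aside for now.

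| Systolic fall (mm Hg) | Heart rate not up by 20 | Heart rate up by 20 |
|---|---|---|
| under 10 | Grades 1 and 2 | Grades 1 and 2 |
| 10 to 19 | Grade 2 | Grades 1 and 2 |
| 20 or more | none | Grade 1 only |

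Illustration: 120/80 falling to 95/65 is a systolic fall of 25. Mean arterial pressure = (systolic + 2 × diastolic)/3 = (95 + 130)/3 = 75, so Grade 3 is not met. This fall has no row grade, or Grade 1 with the heart-rate rise. A fall of 15 meets the Grade 2 bound.

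Now restore the therapy wording. If no need for therapy is required for Grade 1 and correction by oral fluids for Grade 2, that wording can separate the two grades below 10 mm Hg. It adds no systolic criterion at 20 mm Hg or above. A symptom-free fall of 25 corrected by one round of oral fluids would then be Grade 1 on the generic scale, while a fall of 15 corrected in the same way would be Grade 2 by its row.

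**The case against.** The main defence is that nothing is truly ungraded: Table 10 covers all adverse events, and Appendix 1 has its own general row. That stands as to wording, and the claim here is limited to row-specific grades. It does not restore the order, because the general scale is what places a tolerated 1,450 below 2,000.

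A second defence is that the consequences are small. Much of this stands. The WBC reporting resolution is not given. Cohort 1 had no neutropenia in either arm (Table 7). Neutrophil counts have their own halting items 6 and 7, although those are not met by a count of 750/mm³ or more, whatever the total WBC. No postural measurement is scheduled, which limits use of the orthostatic wording. Hypotension Grade 3 has its own criteria, so the defect in Grades 1 and 2 does not alter halting item 4. An untreated, symptom-free fall of 30 would take Grade 1 from the general scale, level with a fall of 8 graded 1, not below it.

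Three stronger readings are tempting and are not supported:

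- A reader might infer that the hypotension row runs backwards. It does not: the cut-offs rise with grade, from 10 to 20. The fault is the missing lower limits.
- A reader might add the Neuromotor row, since Grade 1 has "Mild weakness in muscle of feet, but able to walk; and/or mild increase in reflexes" and Grade 2 has "loss of previously present reflex or development of hyperreflexia", with no mention of a diminished reflex. But the worse finding, loss, is graded, and a tolerated partial reduction falls to Grade 1 on the general scale, which is the right order. Capture of Guillain-Barré syndrome rests on strength examination and the Brighton criteria (Section 8.1.4), where the reflex item is "Decreased or absent deep tendon reflexes in weak limbs" and accompanies limb weakness. It does not rest on this row.
- A reader might express the leukopenia gap as 99 of the 500 counts from 1,000 to 1,499, or about 20%. That counts integers; it says nothing about how often such a result occurs.

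**Conclusion.** Both rows need correction. Leukopenia has a gap at 1,401 to 1,499/mm³; on the general scale a well-tolerated count there ranks below milder leukopenia, and it would not count under halting item 5. Hypotension has no systolic-fall criterion at 20 mm Hg or above, so a larger symptom-free fall can rank below a smaller one; falls under 10 may meet two grades, depending on how the therapy wording is read.

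The size is modest. Few healthy adults should have such values, and only the leukopenia row bears on a halting rule. The leukopenia consequence assumes WBC is reported more finely than 100/mm³. The hypotension consequence assumes mean arterial pressure of at least 60 and no symptoms, IV fluids or hospitalization. Both rest on the digits and signs being as printed. The adjacent Hypertension row shows the opposite sign, which makes a lost symbol less likely but does not exclude it. The documents do not show which leukopenia bound is the slip.

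**What to change.** Reconcile the Leukopenia and Hypotension rows so that the bands are contiguous, do not overlap, and never give a worse value a lower grade. The hypotension row should also make clear whether the therapy wording is part of the criterion. All cut points are for the sponsor's clinical leads to set; none is proposed here.

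Then check Cohort 1 WBC and blood pressure source values against the corrected rows, without reference to treatment assignment, since Cohort 1 events are already tabulated by arm. Table 7 reports neither leukopenia nor hypotension, so it cannot stand in for this check.

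The cost is two table rows in an amendment and a review of existing listings. For WBC, that is at most 28 subjects × 7 scheduled post-dose counts = 196 values through Day 16, plus any optional Day 21 counts. No new measurements are needed.
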